4.7.1.1. Sensitivity Analyses

Sensitivity analyses will be performed on the FAS population by using last observation carried forward (LOCF) imputation methodology to compare the treatment group on Day 84. LOCF will be used to impute missing data for the analysis of covariance (ANCOVA) model with terms for baseline iCFS score and treatment group as covariate. The model assumptions such as Shapiro-Wilk's test of normality; Levene's test of homogeneity of variance will be validated. The estimates of least squares mean for each treatment group and for the difference between treatment groups will be presented together with 95% confidence intervals and two-sided p-value. The sample SAS ANCOVA code would be:

```

PROC GLM DATA= indata;
  CLASS treatment(REF='Vehicle');
  MODEL change = treatment baseline_value;
  LSMEANS treatment / PDIFF CL;
RUN;

```

4.7.2. Secondary Analyses

The secondary efficacy endpoints listed below will be analyzed using repeated measure mixed model by adjusting for covariates that include treatment group, baseline value, visit and interaction term of treatment * visit as the fixed effects. The center will be considered as random effect. The treatment group comparison for each secondary endpoint at each timepoint (Day 84, Day 56, Day 28 and Day 14) will be tested using hierarchical fixed sequence testing followed by the sequential order below:

Statistical Analysis Plan

Sponsor:	VivaVision Biotech, Inc.		
Protocol:	VVN001-CS-201		
Document Version No.:	V3.0	Document Date:	13-JAN-2022

- CFB in eye dryness VAS on Day 84
- CFB in total CFS (tCFS) on Day 84, Day 56, Day 28, Day 14
- CFB in inferior of CFS (iCFS) on Day 56, Day 28, Day 14
- CFB in nasal of CFS on Day 84, Day 56, Day 28, Day 14
- CFB in temporal of CFS on Day 84, Day 56, Day 28, Day 14
- CFB in central of CFS on Day 84, Day 56, Day 28, Day 14
- CFB in superior of CFS on Day 84, Day 56, Day 28, Day 14
- CFB in eye dryness VAS on Day 56, Day 28, Day 14
- CFB in eye discomfort VAS on Day 84, Day 56, Day 28, Day 14
- CFB in SANDE global score on Day 84, Day 56, Day 28, Day 14
- CFB in Schirmer test result on Day 84, Day 56, Day 28, Day 14

For each sequential order of endpoint and each timepoint, the least squares mean (LSMEANS) for each treatment group and the estimated treatment differences for the treatment comparisons (VVN001 5% vs. vehicle and VVM001 1% vs. vehicle) will be reported together with two-sided p-values and 95% 2-sided confidence intervals. The endpoints on study eye and non-study eye will be summarized in the separate model.

The sample code of SAS *PROC MIXED* would be:

```
PROC MIXED DATA=indata;
  CLASS subject center visit treatment(REF='Vehicle');
  MODEL change = treatment visit baseline_value treatment * visit
    /Solution DDFM=KR;
  REPEATED visit / SUBJECT=subject TYPE=UN;
  RANDOM center;
  LSMEANS treatment treatment * visit /PDIFF CL;
  SLICE treatment * visit / SLICEBY=visit PDIFF CL;
RUN;
```

The model convergence and the choice of covariance structure will be handled as similar to the primary analyses mentioned in section 4.7.1.

In addition, the frequency and percentage of subjects achieving a 10-milimeter increase or more in Schirmer test scores from baseline will be presented at each post-baseline visit and any visits

Sponsor:	VivaVision Biotech, Inc.		
Protocol:	VVN001-CS-201		
Document Version No.:	V3.0	Document Date:	13-JAN-2022

by treatment group. The analyses on study eye and non-study eye will be summarized separately. The flag of this achievement will be also reported in the listing. The chi-square test will be performed to compare VVN001 5% versus vehicle and VVM001 1% versus vehicle.

4.8. Safety Analyses

All safety analyses will be conducted on the SAF Population.

4.8.1. Safety Assessments

The following safety assessments will be summarized at each visit if applicable using descriptive statistics for SAF population by treatment group and overall. Assessments will be presented for study eye and non-study eye separately.

- Slit-Lamp biomicroscopy and external eye exam
 - For each anterior segment such as lashes, eyelid, conjunctiva, cornea, anterior chamber, lens pathology and sclera, the summary tabulations of the frequency and percentage for evaluation category such as normal, abnormal CS (clinically significant) and abnormal NCS (non-clinically significant) will be presented. The worsening (from normal to abnormal CS\NCS) change from baseline will be flagged in the data listing.
- Dilated Ophthalmoscopy
 - The evaluation of normal and abnormal for each eye in retina and optic nerve exam will be tabulated by using the frequency and percentage. The cup-to-disc ratio by visits and absolute change from baseline at Visit 6 (Day 84) will be presented using descriptive statistics.
- Intraocular Pressure (IOP) measurement (mmHg)
 - Absolute change from baseline at post-baseline visits will be summarized using descriptive statistics. The frequency and percentage of subjects with increase in $IOP \geq 10$ mmHg from baseline at each post-baseline visits and any visit will be summarized and presented in the data listing as well.
- Best Corrected Visual Acuity (BCVA)
 - LogMAR Visual Acuity (VA) score and change from baseline will be calculated and summarized using descriptive statistics. The frequency and percentage of

Statistical Analysis Plan

Sponsor:	VivaVision Biotech, Inc.		
Protocol:	VVN001-CS-201		
Document Version No.:	V3.0	Document Date:	13-JAN-2022

subjects with loss in VA ≥ 0.3 LogMAR (3 lines) from baseline at each post-baseline visits and any visit will be summarized and presented in the data listing.

- Conjunctival Hyperemia Evaluation
 - Overall bulbar conjunctival hyperemia grading scale: none, very slightly, slight, moderate and severe will be tabulated by using the frequency and percentage for each eye. The worsening (from low to high grading scale) change from baseline will be flagged in the data listing.
- Drop Comfort/Tolerability Assessment
 - The one scored for both eyes on VAS range from 0 to 10 at 1-minute and 5-minute post dose and absolute change from baseline at Visit 6 (Day 84) will be summarized using descriptive statistics.

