14. History of yttrium aluminum garnet-laser posterior capsulotomy or any laser ocular surgery in past 90 days prior to Visit 1.
15. Non-compliance (<80%) with Vehicle Run-In administration.
16. Have had eyelid surgery within the past 6 months.
17. Have a congenitally absent lacrimal gland or meibomian glands.
18. Have had cauterization of the punctum or have had non-dissolvable (silicone) or short term dissolvable punctal plugs inserted or removed within the 30 days prior to the screening or planned during the study. Have had long-term dissolvable plugs within 3 months of Visit 1.
19. Subjects who have active or have had an outbreak of herpetic keratitis within one year of Visit 1 or subjects who are on chronic oral antivirals for herpetic disease.
20. Have a diagnosis of:
 - a. Ongoing ocular infection, lid margin disorders such as blepharitis (including staphylococcal, demodex or seborrheic) are allowed if not requiring treatment with ocular or systemic antibiotics at Visit 1 or intended treatment during the study.
 - b. Meibomian gland disease requiring mechanical meibomian gland expression within the past 3 months
 - c. Excessive lid laxity, floppy eyelid syndrome, ectropion, entropion in either eye, or moderate to severe pinguecula or pterygia in the study eye per the opinion of the Investigator.
 - d. Stevens-Johnson syndrome
 - e. Significant conjunctival scarring in the judgment of the Investigator
 - f. Severe/serious ocular condition that in the judgment of the Investigator opinion could confound study assessments or limit compliance.
 - g. Severe/serious systemic disease or uncontrolled medical condition that in the judgment of the Investigator could confound study assessments or limit compliance.
21. Have a documented history of ocular allergies, which, in the judgment of the Investigator, are likely to have an acute increase in severity due to the expected timing of the exposure to the allergen to which the subject is sensitive. Subjects sensitive to seasonal allergens that are not expected to be present during the study are permitted.

22. Be current cigarette smokers.
23. Have been exposed to an investigational drug within the preceding 30 days or previously randomized in this study.
24. Be an employee of the site that is directly involved in the management, administration, or support of this study or be an immediate family member of the same.
25. Have a known history of alcohol and/or drug abuse within the past 5 years.

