APPENDIX 5: SLIT-LAMP BIOMICROSCOPY

The biomicroscopy exam should be performed with the slit lamp using a beam width and intensity that provide optimal evaluation of the anterior segment.

This procedure will be performed in the same manner for all subjects observed at the Investigator's site. The site will record all ABNORMAL findings in the source document and the Investigator will evaluate the ABNORMAL findings as Non-Clinically Significant (NCS) or Clinically Significant (CS). CS and NCS ABNORMAL findings will be recorded in the source documentation. However, only ABNORMAL CS descriptions will be captured in the eCRF.

Lashes

- 0 = Normal
- 1 = Abnormal

Eyelid

Edema

- 0 = Normal, no swelling of the lid tissue
- 1 = Abnormal

Skin

- 0 = Normal, including but not limited to thinning, pigment changes, dermatitis
- 1 = Abnormal

Conjunctiva

Edema

- 0 = Normal, no swelling of the conjunctiva
- 1 = Abnormal

Cornea

Infiltrates

- 0 = Absent
- 1 = Present

Endothelial Changes

- 0 = Normal, None
- 1 = Abnormal, pigment, keratoprecipitates, guttata

Edema

- 0 = Normal, None, transparent and clear
- 1 = Abnormal

Anterior Chamber

Cells

- 0 = Normal, No cells seen
- 1 = Abnormal (+ to +++ cells)

Flare

- 0 = Normal, No Tyndall effect
- 1 = Abnormal, Tyndall beam in the anterior chamber

Lens Pathology

- 0 = Normal, no opacity in the lens
- 1 = Abnormal, existing opacity in the lens; aphakic or pseudophakic eyes or other abnormal findings

Sclera

- 0 = Normal
- 1 = Abnormal

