Table 14.3.2.3	Ocular Serious Treatment-Emergent Adverse Events (TEAEs) by System Organ Class and Preferred Term – SAF
Table 14.3.2.4	Non-Ocular Serious Treatment-Emergent Adverse Events (TEAEs) by System Organ Class and Preferred Term – SAF
Table 14.3.3.1	The Most Severity of Ocular Treatment-Emergent Adverse Events (TEAEs) by System Organ Class and Preferred Term – SAF
Table 14.3.3.2	The Most Severity of Non-Ocular Treatment-Emergent Adverse Events (TEAEs) by System Organ Class and Preferred Term – SAF
Table 14.3.4.1	The Strongest Relationship of Ocular Treatment-Emergent Adverse Events (TEAEs) to Study Drug by System Organ Class and Preferred Term – SAF
Table 14.3.4.2	The Strongest Relationship of Non-Ocular Treatment-Emergent Adverse Events (TEAEs) to Study Drug by System Organ Class and Preferred Term – SAF
Table 14.3.5.1	Summary of Slit-Lamp Biomicroscopy Results on Study Eye by Location and Visit – SAF
Table 14.3.5.2	Summary of Slit-Lamp Biomicroscopy Results on Non-Study Eye by Location and Visit – SAF
Table 14.3.6.1	Summary of Dilated Ophthalmoscopy Results on Study Eye by Visit – SAF
Table 14.3.6.2	Summary of Dilated Ophthalmoscopy Results on Non-Study Eye by Visit – SAF
Table 14.3.7.1	Summary of Intraocular Pressure (mmHg) Results and Change from Baseline on Study Eye by Visit – SAF
Table 14.3.7.2	Summary of Intraocular Pressure (mmHg) Results and Change from Baseline on Non-Study Eye by Visit – SAF
Table 14.3.8.1	Summary of Best Corrected Visual Acuity (BCVA) LogMAR Score and Change from Baseline on Study Eye by Visit – SAF

Statistical Analysis Plan

Sponsor:	VivaVision Biotech, Inc.		
Protocol:	VVN001-CS-201		
Document Version No.:	V3.0	Document Date:	13-JAN-2022

Table 14.3.8.2	Summary of Best Corrected Visual Acuity (BCVA) LogMAR Score and Change from Baseline on Non-Study Eye by Visit – SAF
Table 14.3.9.1	Achieving More than 10 mmHg Increase in Intraocular Pressure (IOP) from Baseline on Study Eye by Visit – SAF
Table 14.3.9.2	Achieving More than 10 mmHg Increase in Intraocular Pressure (IOP) from Baseline on Non-Study Eye by Visit – SAF
Table 14.3.10.1	Loss of More than 3 Lines in Best Corrected Visual Acuity (BCVA) LogMAR Score from Baseline on Study Eye by Visit – SAF
Table 14.3.10.2	Loss of More than 3 Lines in Best Corrected Visual Acuity (BCVA) LogMAR Score from Baseline on Non-Study Eye by Visit – SAF
Table 14.3.11	Summary of Comfort/Tolerability VAS and Change from Baseline by Visit – SAF

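### SAP 4.8.1 flags slit-lamp worsening only from normal to abnormal, so a change from abnormal NCS to abnormal CS gets no worsening flag

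*SAP*

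**What the plan says.** SAP 4.8.1 (Safety Assessments) plans frequencies for each anterior-segment structure, with "evaluation category such as normal, abnormal CS (clinically significant) and abnormal NCS (non-clinically significant) will be presented". These are given by visit and treatment group, separately for the study and non-study eye. The change rule follows: "The worsening (from normal to abnormal CS\NCS) change from baseline will be flagged in the data listing".

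For conjunctival hyperemia the same section uses a different rule: "The worsening (from low to high grading scale) change from baseline will be flagged in the data listing".

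The table list in SAP 7.1 has two slit-lamp tables. Table 14.3.5.1 is titled "Summary of Slit-Lamp Biomicroscopy Results on Study Eye by Location and Visit", and Table 14.3.5.2 is its counterpart for the non-study eye. No shift table is listed. For IOP and BCVA, SAP 4.8.1 instead plans the number and percentage of subjects crossing a change-from-baseline threshold at each post-baseline visit and at any visit (Tables 14.3.9.1-2 and 14.3.10.1-2).

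Protocol Appendix 5 has the investigator grade every abnormal slit-lamp finding as NCS or CS. On data capture it says: "However, only ABNORMAL CS descriptions will be captured in the eCRF".

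**The concern.** The three categories have a natural order, and the rule recognises worsening only when a structure leaves normal. A structure that starts as NCS and is later judged CS has worsened in the investigator's own grading, yet gets no flag. A structure that goes from normal to a trivial NCS finding does get one. The rule therefore marks the smaller change and passes over one that the investigator considers clinically significant.

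Some eyes can be expected to start abnormal. Exclusion 20a in Protocol 4.2 says "lid margin disorders such as blepharitis (including staphylococcal, demodex or seborrheic) are allowed", provided no antibiotic treatment is needed. Exclusion 13 bars intraocular surgery only within 12 months of Visit 1, and Appendix 5 scores as lens abnormality any opacity and "aphakic or pseudophakic eyes or other abnormal findings".

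At stake is the reading of a named safety endpoint. SAP 1.2.1 makes safety and tolerability against vehicle the primary objective.

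**Working it through.** The plan gives no figure to reproduce. The check is to list the possible changes and apply each rule as written.

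**1. Slit-lamp rule (SAP 4.8.1).** Three ordered categories allow 3 × 2 / 2 = 3 upward moves.

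| Baseline | Later visit | Flagged? |
|---|---|---|
| Normal | Abnormal NCS | Yes |
| Normal | Abnormal CS | Yes |
| Abnormal NCS | Abnormal CS | No |

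The rule covers 2 of 3.

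**2. Hyperemia rule (same section).** The scale in Protocol Appendix 3 has five grades, 0 to 4, so there are 5 × 4 / 2 = 10 upward moves. A rule that flags any move from a lower to a higher grade covers all 10. Read the same way, the slit-lamp rule would cover 3 of 3.

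**3. Do the tables fill the gap?** Only in part. When an eye goes from NCS to CS, the NCS count in its arm falls by one and the CS count rises by one. Two limits remain.
- The counts are marginal. If one eye goes from NCS to CS while another in the same arm goes from CS to NCS, the counts do not change although one eye has worsened.
- The counts are by visit. One CS finding at Day 14 and one at Day 28 may be one subject or two, and the table cannot say which.

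**4. Does adverse event reporting fill the gap?** The treatment-emergent definition in SAP 4.8.2 includes events present at baseline that become more severe. Neither document says that a slit-lamp change from NCS to CS must be reported as an adverse event, so this route is open but not assured.

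**5. Size.** Among structures not already CS at baseline, let p be the share that are NCS, and let a and b be the chances of becoming CS from NCS and from normal. The share of new CS findings without a flag is p·a / (p·a + (1 − p)·b). If a = b, this reduces to p: assuming p = 20%, 40% or 60% simply returns 20%, 40% or 60%. The documents give none of p, a or b, so these values illustrate the formula and estimate nothing about this trial.

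**6. Level of application.** The SAP tabulates by segment, such as cornea, while Appendix 5 scores several items within the cornea (infiltrates, endothelial changes, edema). If the flag is derived per segment, a baseline NCS endothelial finding would also block the flag for new CS corneal edema. The SAP does not say which level applies.

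**The case against.** The strongest reply is that the sentence governs only an annotation in a listing. The SAP counts no slit-lamp worsening of any kind, so no table loses a case through this rule. CS is tabulated separately from NCS by arm and visit, so an arm-level excess of CS findings would show. Listing 16.2.9.1 covers the examination, and Protocol 9.1.4 makes treatment-emergent adverse events the primary safety analysis. All of this stands, and it limits the weight of the point.

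A reader might infer that structures abnormal at baseline can never show harm. The documents do not support that, because those structures still enter the CS row and may give rise to an adverse event.

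A reader might also infer that baseline abnormality will be common and that a known share of harm goes unseen. That is not supported either. Inclusion 11 requires normal lid anatomy, and exclusions 20c, 20e and 20f remove lid malposition, significant conjunctival scarring and severe ocular conditions. Appendix 5 has no lid-margin or blepharitis item, so allowing blepharitis does not show how often its lid items will be abnormal. Aphakia and pseudophakia are fixed states and do not show that progression to CS is likely.

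The objection does not remove the gap itself. The flag is the only slit-lamp output defined as change from an eye's own baseline, and as written it omits one of three upward moves.

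**Conclusion.** The point holds in limited form. Followed exactly, SAP 4.8.1 leaves a move from abnormal NCS to abnormal CS without a worsening flag, inconsistent with the hyperemia rule beside it. No slit-lamp table compares worsening between arms. The conclusion assumes that the parenthesis in the rule is meant as its definition and that the three categories are ordered by clinical importance.

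The size is unknown, because the documents give no baseline NCS prevalence. This is a gap in descriptive safety reporting. It is worth correcting because safety is the SAP's primary objective and the correction is cheap.

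**What to change.** - **First confirm the data.** Check that the NCS category itself, and not only the text of CS findings, is in the eCRF. The sentence in Appendix 5 leaves this open. The existing three-category tabulation needs the category as much as a wider flag does. If it is not captured, both need attention.
- **Change the rule in SAP 4.8.1.** Define worsening per structure as any increase from baseline along normal < abnormal NCS < abnormal CS. State whether a structure means the SAP's segment or the Appendix 5 item.
- **Add to Tables 14.3.5.1 and 14.3.5.2.** Give either a baseline-to-visit shift, or the number and percentage of subjects with any worsening and with worsening to CS, by arm, at each visit and at any visit. The second form follows what is already planned for IOP and BCVA.
- **Optional.** Add a matching count of hyperemia worsening to Tables 14.3.12.1 and 14.3.12.2. The hyperemia rule itself needs no correction.

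If NCS status is in the database, the cost is one phrase and some derived rows, with no new assessments. The small downside is that more subjects will be shown as worsened.

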4.8.2. Adverse Events

Adverse events will be coded using the Medical Dictionary for Regulatory Activities (MedDRA) and displayed in tables and listings using System/Organ/Class (SOC) and Preferred Term (PT).

Analyses of adverse events will be performed for those events that are considered treatment emergent, where treatment emergent is defined as any adverse event with onset after the first dose of study medication through the end of the study or any event that was present at baseline but worsened in severity.

Adverse events are summarized by subject incidence rates, therefore, in any tabulation, a subject contributes only once to the count for a given adverse event (SOC or preferred term) by treatment group and overall. In summary tables, SOC will be presented alphabetically and events within SOC will be presented by decreasing frequency count based on the total column.

The frequency and percentage of subjects with any treatment-related ocular and non-ocular TEAE, with any TEAE assessed by the Investigator as related to treatment (definite, probable, or possible relationship), with any TEAE by severity (mild, moderate or severe), and with any serious adverse event (SAE) will be summarized by treatment group and overall. In these tabulations, each subject will contribute only once (i.e., the most related occurrence or the most severe occurrence) to each of the incidence rates in the descriptive analysis, regardless of the frequency of episodes. Furthermore, the frequency and percentage of subjects with any TEAEs by outcome, with any TEAEs by action taken, with any TEAEs by action taken related to study drug will be also summarized in the table by treatment group and overall. Separate summaries will be performed for ocular and non-ocular TEAEs by the most severity and strongest relationship by SOC and PT by treatment group and overall.

Sponsor:	VivaVision Biotech, Inc.		
Protocol:	VVN001-CS-201		
Document Version No.:	V3.0	Document Date:	13-JAN-2022

No formal hypothesis-testing analysis of adverse events incidence rates will be performed.

All adverse events occurring on study will be listed in subject data listings.

By-subject listings also will be provided for the following: subject deaths; serious adverse events; and adverse events leading to withdrawal.

4.8.3. Laboratory Data

Safety laboratory tests will be collected in the central laboratory at Visit 1 and Visit 6. The actual continuous value and change from Visit 1 to Visit 6 will be summarized for each clinical laboratory parameter, including hematology, clinical chemistry, and urinalysis . All laboratory data will be provided in data listings. Urine pregnancy test results will be captured at Visit 1 and Visit 6. Urine pregnancy test results will be provided in data listing.

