5. STUDY DISCONTINUATION/PARTICIPANT WITHDRAWAL

5.1. PARTICIPANT DISCONTINUATION/WITHDRAWAL FROM THE STUDY

Any subject who wishes to discontinue the IP use or withdraw from participation in the study for any reason is entitled to do so without obligation. The Investigator may also discontinue any subject from the IP use or from study participation, if deemed necessary.

Investigational Product use may be discontinued, and any subject may be discontinued from study participation at any time during the study at the discretion of the Investigator or the Sponsor for any reason including but not limited to:

1. Occurrence of any medical condition or circumstance that exposes the subject to substantial risk and/or does not allow the subject to adhere to the requirements of the protocol.
2. Any Serious Adverse Event (SAE), clinically significant AE, severe laboratory abnormality, intercurrent illness, or other medical condition that indicates to the Investigator that continued participation is not in the best interest of the subject.
3. Subject's decision to withdraw.
4. Any woman who becomes pregnant while participating in the study. Information on the pregnancy and outcome will be requested.
5. Subject's failure to comply with protocol requirements or study related procedures.
6. Termination of the study by the Sponsor, Food and Drug Administration (FDA), or other regulatory authorities.

In the event study discontinuation of a randomized subject is necessary, the Investigator should make every attempt to have the subject complete Visit 6 assessments as possible. If a non-serious AE is unresolved at the time of the subject's final study visit, an effort will be made to follow up until the AE is resolved or stabilized, the subject is lost to follow-up, or there is some other resolution of the event. The Investigator should make every attempt to follow all SAEs to resolution. The reason for premature discontinuation should be entered into the eCRF and recorded in the subject chart.

Subjects who withdraw from the study will not be replaced.

Additionally, the trial or parts of the trial may be discontinued by the Sponsor or at the recommendation of the Investigator after consultation with VivaVision Biotech, Inc. This may be based on a significant number of AEs of a similar nature that warrant such action.

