Table 14.3.12.1	Summary of Conjunctival Hyperemia Grading Scale on Study Eye by Visit – SAF
Table 14.3.12.2	Summary of Conjunctival Hyperemia Grading Scale on Non-Study Eye by Visit – SAF
Table 14.3.13.1	Summary of Hematology Results and Change from Screening by Visit – SAF
Table 14.3.13.2	Summary of Chemistry Results and Change from Screening by Visit – SAF
Table 14.3.13.3	Summary of Urinalysis Results and Change from Screening by Visit – SAF

Statistical Analysis Plan

Sponsor:	VivaVision Biotech, Inc.		
Protocol:	VVN001-CS-201		
Document Version No.:	V3.0	Document Date:	13-JAN-2022

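### Laboratory safety data are summarised only as continuous values and change from Visit 1 to Visit 6, with no shift table or by-arm count of out-of-range results

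*SAP*

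**What the plan says.** SAP 4.8.3 fixes the timing ("Safety laboratory tests will be collected in the central laboratory at Visit 1 and Visit 6") and the method: "The actual continuous value and change from Visit 1 to Visit 6 will be summarized for each clinical laboratory parameter, including hematology, clinical chemistry, and" (last item: urinalysis). It adds that "All laboratory data will be provided in data listings". SAP 4.2.1 defines a continuous summary as n, mean, median, standard deviation, minimum and maximum.

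The table list in SAP 7.1 matches. Table 14.3.13.1 is titled "Summary of Hematology Results and Change from Screening by Visit", Table 14.3.13.3 is titled "Summary of Urinalysis Results and Change from Screening by Visit", and Table 14.3.13.2 does the same for chemistry. The laboratory listings are 16.2.9.8.1 to 16.2.9.8.3.

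The protocol mentions laboratory abnormality once. Section 5.1 includes it among the reasons for which treatment or participation may be stopped at discretion: "clinically significant AE, severe laboratory abnormality, intercurrent illness". The term is neither defined nor graded. Laboratory results are not among the safety endpoints in Protocol 2.2.1 or the safety variables in SAP 2.4.1.

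**The concern.** A laboratory safety signal may consist of a few subjects with large changes while everyone else is unaffected. Summaries of location are insensitive to that pattern, and a minimum or maximum describes one subject per arm. The question a safety reader asks first is how many subjects in each arm moved out of range, and no planned table answers it.

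The gap stands out for two reasons. SAP 1.2.1 makes safety and tolerability the primary objective, and SAP 4.8.4 says vital signs and physical examinations are not collected. Laboratory tests are therefore the main objective systemic safety data in the trial. At stake is a study report with similar mean changes across arms that does not show whether abnormal results cluster on active drug.

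Urinalysis raises a smaller point. A value and a change suit numeric items only. If the panel includes graded or non-numeric items, SAP 4.2.1 would give category counts by visit but no shift from Visit 1.

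**Working it through.** **1. What SAP 4.8 plans for each safety measure**

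| Measure | Per-subject category or count | Listing |
|---|---|---|
| Slit lamp | normal / abnormal CS / abnormal NCS | worsening flagged |
| Dilated ophthalmoscopy | normal / abnormal | no flag stated |
| IOP | rise of 10 mmHg or more | presented |
| BCVA | loss of 0.3 LogMAR or more | presented |
| Conjunctival hyperemia | five grades | worsening flagged |
| Drop comfort | none (0 to 10 scale) | no flag stated |
| Laboratory | none | all values, no flag stated |

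For IOP the SAP asks explicitly for "The frequency and percentage of subjects with increase in" pressure beyond a threshold, in addition to mean change. Laboratory data are the only measure with natural normal limits that gets no such treatment.

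**2. Other routes to a count**

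- *Adverse events.* SAP 4.8.2 reports subject incidence by arm. The definition in Protocol 8.1.1 is broad enough to cover a laboratory abnormality that an investigator reports. However, Protocol 8.1.2 elicits events by asking how the subject has felt, and no text says when a laboratory result becomes an event.
- *Discontinuation reasons.* SAP 4.4 summarises these by arm. The only scheduled post-dose draw is at Visit 6, the exit visit (Protocol 6.1.6 and Appendix 1), or at an early-termination visit that repeats the Visit 6 assessments (Protocol 6.1.7). By then the subject is leaving, so a scheduled result will rarely be the reason.
- *Early-termination results.* SAP 4.2.9 uses nominal visits and maps early-termination visits only for the primary and key secondary efficacy endpoints. A dropout's last laboratory result may therefore be missing from the change to Visit 6.

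**3. Illustration of how little the mean moves**

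The plan gives no laboratory incidence or threshold to reproduce. Its only relevant figure is 55 per arm (SAP 4.1). That reproduces for iCFS as 2 × (1.960 + 0.842)² × 0.80² / 0.43² = 54.3, rounded up to 55. It serves here only as the arm size.

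Assumptions, none from the documents: change has SD 1 in unaffected subjects; k of 55 subjects in one active arm shift by s SD; nobody on vehicle shifts.

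- Mean shift = k·s/55
- Arm variance = 1 + (k/55)(1 − k/55)s²
- SE of the difference = √((arm variance + 1)/55)
- Median shift (large s) = Φ⁻¹(0.5/(1 − k/55))

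For k = 3, s = 4:
- Mean shift = 12/55 = 0.218
- Arm variance = 1 + 0.0545 × 0.9455 × 16 = 1.825, so the arm SD is 1.35
- SE = √(2.825/55) = 0.227
- Ratio of mean shift to SE = 0.96
- Median shift = Φ⁻¹(0.529) = 0.07

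| k | s | Mean shift (SD) | Mean shift / SE |
|---|---|---|---|
| 2 | 3 | 0.109 | 0.53 |
| 2 | 5 | 0.182 | 0.80 |
| 3 | 4 | 0.218 | 0.96 |
| 4 | 3 | 0.218 | 1.00 |
| 4 | 5 | 0.364 | 1.40 |

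The SAP plans no test of laboratory data. The last column is only a ruler for how visible the shift would be next to ordinary sampling noise.

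**The case against.** The other side has several fair points.

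- A reader might infer that laboratory abnormalities will have no incidence in any arm. The documents do not support that. Abnormalities reported as adverse events are counted by arm, and discontinuation reasons are tabulated by arm. What is missing is a systematic count taken from the laboratory data.
- A reader might also take Protocol 5.1 to make severe laboratory abnormality a harm that the trial set out to measure. It is an undefined, discretionary ground for stopping, not an endpoint. An out-of-range count would not measure it, because out of range is not the same as severe.
- IOP and BCVA are named safety endpoints and laboratory results are not. Giving the ocular endpoints of a topical Phase 2a trial more detail is a choice, not a contradiction.
- The planned tables hold more than means. In the example the active-arm SD would print as 1.35 against 1.00 on vehicle, beside an extreme minimum or maximum.
- The illustration is built entirely on assumptions. A 4 SD change need not cross a reference limit, and vehicle subjects will have incidental crossings. Even 3/55 against 0/55 has a two-sided Fisher p of about 0.24 (2 × C(55,3)/C(110,3) = 2 × 26,235/215,820).
- Protocol 1.2 says the drug binds a leukocyte surface antigen, but no passage identifies a hematologic risk or gives systemic exposure. The urinalysis items are not listed either, so non-numeric ones are only a possibility.

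All of this limits the claim, and none of it supplies the count. An inflated SD or an extreme maximum tells the reader to look further without saying how many subjects are affected. The adverse-event route depends on each investigator's judgement.

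**Conclusion.** The point holds as a gap in descriptive safety reporting. SAP 4.8.3 and Tables 14.3.13.1 to 14.3.13.3 contain no range classification, shift table or by-arm count of out-of-range results. The frequency of laboratory abnormalities by arm can be seen only through investigator-reported events or by counting from listings with no planned flag. That second inference rests on the SAP text and listing titles, since no listing shells are given.

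Its size cannot be stated from the documents. Under the assumptions above, 2 to 4 affected subjects of 55 would move the arm mean by 0.5 to 1.4 standard errors of the between-arm difference, which is easy to overlook. A count would also be imprecise at this arm size: 3/55 is 5.5% (95% Clopper-Pearson interval 1.1% to 15.1%), and 0/55 has an upper limit of 6.5%. The purpose is to make cases visible, not to test them. Nothing here affects efficacy, alpha or sample size, so this is a cheap improvement, not a flaw that threatens the trial's conclusions.

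**What to change.** In SAP 4.8.3, keep the continuous summaries and add the following on the SAF, by arm:

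- For hematology and chemistry, a low/normal/high shift table against the central laboratory's reference range, from Visit 1 to the last post-dose value. Using the last value keeps early-termination results in the table.
- The number and percentage of subjects with a new out-of-range value, per parameter.
- Category shifts for any urinalysis items that are not numeric, in place of a value and change.
- A flag for new out-of-range values in Listings 16.2.9.8.1 to 16.2.9.8.3.

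Add a count of clinically significant results only if the eCRF collects that rating for laboratory data. The documents specify such a rating only for slit-lamp findings (Protocol Appendix 5, SAP 4.8.1).

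The cost is some SAP wording and a few extra tables. No new test or visit is needed. The documents do not say that reference ranges are held in the database, so they may have to be obtained from the central laboratory. The downside is some incidental out-of-range counts to explain in the report.
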